##### **4.7.2.2. Other Secondary Efficacy Endpoints**

The other secondary efficacy endpoints are:

- The percent change in non-HDL-C from baseline to week 52
- The percent change in TC from baseline to week 52
- The percent change in ApoB48 from baseline to week 52
- The percent change in ApoB100 from baseline to week 52

- The percent change in NMR-determined particle size and number (biomarkers of TG-rich lipoprotein metabolism) from baseline to week 52
- Number of independently adjudicated episodes of AP per patient during 52 weeks of the DBTP

#### **4.7.3. Exploratory Efficacy Endpoints**

The exploratory efficacy endpoints are:

- Proportion of patient responders during 52 weeks of therapy with evinacumab versus placebo, with response defined as reaching common clinical TG thresholds of  $\leq 880$  mg/dL,  $\leq 500$  mg/dL,  $\leq 150$  mg/dL
- Length of stay for AP hospitalizations during 52 weeks of therapy with evinacumab versus placebo
- Proportion of abdominal pain-free intervals during 52 weeks of therapy with evinacumab versus placebo, measured via a single-item questionnaire
- Mean change in abdominal pain scores on the Hypertriglyceridemia and Acute Pancreatitis: Pain Questionnaire (HAP-Pain) during 52 weeks of therapy with evinacumab versus placebo

### **4.8. Safety Variables**

The safety variables in this study include:

- TEAEs
- Routine safety laboratory tests (hematology, chemistry, urinalysis, and pregnancy testing [for women of childbearing potential or WOCBP])
- Vital signs
- Electrocardiogram (ECG)
- Physical examination

#### **4.8.1. Adverse Events Variables**

The period of safety observation starts from the time when the patient gives informed consent and continues into the following periods:

- The pre-treatment period is defined from the day the ICF is signed to the day before the first dose of study treatment administration.
- The treatment-emergent adverse event (TEAE) period is defined from the day of the first study treatment administration to the day of the last study treatment administration + 168 days (24 weeks).
- The post-treatment period is defined from the day after the end of the TEAE period to the last study visit.

#### **4.8.1.1. Adverse Events and Serious Adverse Events**

Adverse events (including serious adverse events (SAE), AEs causing permanent treatment discontinuation, deaths, and AEs of special interest) are recorded from the time of signed informed consent until the end of study. All AEs diagnosed by the Investigator will be reported and described.

All AEs will be dictionary coded by “lowest level term (LLT)”, “preferred term (PT)”, “high level term (HLT)”, “high level group term (HLGT)” and associated primary “system organ class (SOC)” using the version of MedDRA in effect at the time of the first database lock.

##### ***Adverse Event Observation Period***

- Pre-treatment AEs are AEs that developed or worsened or became serious during the pre-treatment period.
- TEAEs are AEs that developed or worsened or became serious during the TEAE period.
- Post-treatment AEs are AEs that developed or worsened or became serious during the post-treatment period.

#### **4.8.1.2. Adverse Events of Special Interest**

Adverse events of special interest (AESI) are AEs (serious or non-serious) required to be monitored, documented, and managed in a pre-specified manner. AESIs will be recorded on the adverse event e-CRF using dedicated tick boxes.

The AESIs include the following:

- Anaphylactic reactions
- Moderate/severe infusion reactions
- Allergic reactions that require medical treatment or consultation with another physician for further evaluation
- Increase in ALT or AST:  $\geq 3x$  ULN (if baseline  $<$ ULN), or  $\geq 2x$  baseline value (if baseline  $\geq$ ULN)

#### **4.8.1.3. Other AEs Require Reporting to the Sponsor**

The other AEs which require reporting to the sponsor (or designee) within 24 hours of learning of the event are:

- Pregnancy: Although pregnancy is not considered an AE, it is the responsibility of the investigator to report to the sponsor (or designee), within 24 hours of identification, any pregnancy occurring in a female patient during the study or within 24 weeks of the last dose of study drug. Any complication of pregnancy affecting a female study patient and/or fetus and/or newborn that meets the SAE criteria must be reported as an SAE. Outcome for all pregnancies should be reported to the sponsor.

- Symptomatic overdose with study drug: Accidental or intentional overdose of at least 2 times the intended dose of study drug within the intended therapeutic window, if associated with an AE.

#### **4.8.1.4. Events Causing Death**

The observation periods for patient deaths are per the observation periods defined above.

- Death on-treatment: deaths occurring during the TEAE period,
- Death post-treatment: deaths occurring during the post-treatment period.

#### **4.8.2. Laboratory Safety Variables**

Clinical laboratory tests will consist of blood analyses (including hematology, clinical chemistry and other). Clinical laboratory values will be converted and analyzed in both international units and US conventional units, with associated normal ranges provided by the central laboratory. Both actual test values and “change from baseline” values (defined as the post-baseline value minus the baseline value) will be used in the result summaries. Potentially clinically significant values (PCSV) ranges will be applied to the laboratory test values as applicable (see Appendix 10.3 for PCSV definitions). For those laboratory tests that do not have PCSV ranges, central laboratory normal ranges will be applied to identify out-of-range values. All laboratory test samples will be collected before study treatment administration during the protocol scheduled visits.

Unless otherwise specified below, blood samples for clinical laboratories will be collected at the protocol scheduled visits, and visits will be assigned to the Global Analysis Windows (See Appendix 10.2). The laboratory parameters (excluding those considered as efficacy parameters) will be classified as follows:

##### Hematology:

- Red blood cells and platelets: hemoglobin, hematocrit, erythrocytes count, platelets count, red blood indices
- White blood cells: white blood cells, neutrophils, lymphocytes, monocytes, basophils, eosinophils

##### Clinical chemistry:

- Metabolism: glucose, total protein, albumin, creatine phosphokinase, HbA1c
- Electrolytes: sodium, potassium, chloride, calcium, bicarbonate
- Renal function: creatinine, blood urea nitrogen (BUN), uric acid
- Liver function: ALT, aspartate aminotransferases (AST), alkaline phosphatase (ALP), total bilirubin, LDH

#### **4.8.3. Vital Signs Variables**

Vital signs variables will include height (cm), weight (kg), heart rate (bpm), respiration (rpm), temperature (C or F), systolic and diastolic blood pressure (mmHg) after resting at least five minutes. Both actual test values and “change from baseline” values (defined as the post-baseline

value minus the baseline value) will be provided for protocol specified visits and visits will be assigned to the Global Analysis Windows (See Appendix 10.2). Potentially clinically significant values (PCSV) ranges will be applied to the vital sign parameter values as applicable (see Appendix 10.3 for PCSV definitions).

#### **4.8.4. 12-Lead Electrocardiography (ECG) Variables**

Electrocardiograms will be performed before blood samples are collected at visits requiring blood draws. A standard 12-lead ECG will be performed at specified time points according to Appendix 10.4. The ventricular rate, PR, QRS, RR, QT, QTcF, and QTcB intervals will be recorded. Electrocardiogram assessments will be described as normal or abnormal, and visits will be assigned to the Global Analysis Windows (See Appendix 10.2).

#### **4.8.5. Physical Examination Variables**

Physical examination will be conducted at the protocol scheduled visits (See Appendix 10.4 for schedule of events). The visits will be assigned to the Global Analysis Windows (See Appendix 10.2).

### **4.9. Pharmacokinetic Variables**

Pharmacokinetic (PK) variables include total evinacumab concentrations and total ANGPTL3 concentrations collected at each specified time point (both pre-dose and end-of-infusion samples) specified in Appendix 10.4.

### **4.10. Immunogenicity Variables**

Anti-drug antibody variables will include ADA status, titer and time-point/visit. Serum samples for ADA will be collected at the clinic visits specified in Appendix 10.4. Considering the few patients enrolled in the study due to the early termination of the protocol, samples positive in the ADA assay will be characterized for ADA titers, but NAb analyses will not be performed.

### **4.11. Pharmacodynamic and Other Biomarker Variables**

The pharmacodynamic (PD) variables in this study are high-density lipoprotein cholesterol (HDL-C) and LDL-C.

ApoC3, ApoB48, ApoB100, and NMR-determined particle size and number are biomarkers of TG-rich lipoprotein metabolism and are also efficacy variables in this study.

## **5. STATISTICAL METHODS**

In general, demographic, baseline characteristics, and medical history will be summarized and presented in treatment groups and overall for the study in the safety analysis set. The exposure, prior and concomitant medications, and the safety data will be summarized and presented in treatment groups for the safety analysis set. The efficacy data will be summarized and presented in treatment groups for the ITT analysis set.

Continuous data will be summarized descriptively using the number of patients with data, mean, SD, median, minimum and maximum for each treatment group for the study. First quartile (Q1) and third quartile (Q3) will be also provided for baseline lipid parameters, HbA1c.

Categorical and ordinal data will be summarized using the number and percentage of patients for each treatment group for the study.

### **5.1. Demographics and Baseline Characteristics**

Demographic and baseline characteristics will be summarized descriptively by treatment group and overall for the study in the safety analysis set.

Parameters listed in Section 4.1 will be summarized as described. As applicable, other safety baseline data not listed in Section 4.1 will be presented collectively in the descriptive statistics summary tables containing respective post-baseline data.

### **5.2. Medical History**

Medical history will be descriptively summarized by treatment group and overall for the study in the safety analysis set.

All reported patient's medical history will be presented by primary SOC and HLT. The tables will be presented by SOC sorted alphabetically and decreasing patient frequency of HLT based on the overall incidence in the study.

In addition, acute pancreatitis history and cardiovascular history will be summarized by treatment group. Continuous data will be summarized using the number of patients with data, mean, SD, median, Q1, Q3, minimum and maximum for the study and for each of the treatment groups. Categorical and ordinal data will be summarized using the number and percentage of patients in the study and for each of the treatment groups.

### **5.3. Prior and Concomitant Medications**

All prior medications, dictionary coded by WHO-DD, will be descriptively summarized by treatment group for the study in the safety analysis set. Summaries will present patient counts and percentages for all prior medications, by decreasing frequency of the overall incidence of ATC followed by therapeutic class. In case of equal frequency across anatomical or therapeutic categories, alphabetical order will be used. Patients will be counted once in each ATC category (anatomical or therapeutic) linked to the medication, but may be counted several times for the same medication.

All concomitant medications during the study, dictionary coded by WHO-DD, will be descriptively summarized by treatment group for the study. Summaries will present patient counts and percentages for all concomitant medications, by decreasing frequency of the evinacumab group incidence of ATC followed by therapeutic class. In case of equal frequency across anatomical or therapeutic categories, alphabetical order will be used. Patients will be counted once in each ATC category (anatomic or therapeutic) linked to the medication, hence may be counted several times for the same medication. Additionally, concomitant lipid lowering treatment (LLT) use will also be summarized by patient counts and percentages.

#### **5.4. Prohibited Medications**

Listing of prohibited medications will be provided for the patients in the safety analysis set for the study.

#### **5.5. Patient Disposition**

Patient disposition includes the description of patient status at major milestone decisions in the study.

Patient study status for the study will be summarized by treatment group for the study (screened patients, screen failures, and non-enrolled but treated patients only). Summaries will provide the frequency (and percentage as applicable) of patients that met the criteria for the variables described in Section 4.5. Exception listings will be generated for any patient treated but not enrolled, enrolled but not treated.

All patient analysis populations will be summarized by treatment group for the study, depicting frequencies (and percentages) of patients that met the criteria for each population described in Section 3.

The summary of patient disposition will be provided for all patients in the study.

#### **5.6. Extent of Study Treatment Exposure and Protocol Deviations**

The extent of study treatment exposure and compliance for the study described in Section 4.6 will be assessed and summarized by treatment group for the study, for patients in the safety analysis set.

##### **5.6.1. Exposure to Investigational Product**

Study treatment exposure in the study will be descriptively summarized for treatment duration and total number of infusions as described in Section 4.6. Treatment duration (including patient-years) and total number of infusions will be summarized using the number of patients with data, mean, SD, Q1, Q3, median, minimum and maximum. Categorized 4-week intervals of treatment duration will be summarized descriptively by counts and percentages.

##### **5.6.2. Protocol Deviations**

Both monitored and derived protocol deviations will be summarized for important deviations (counts of deviations), patients (incurring a deviation by count and percentage), and by type of important deviation (patient count and percentage). A patient listing of all important and minor protocol deviations will be provided.

## **5.7. Analyses of Efficacy Variables**

For statistics where international and conventional units do not impact the results (e.g. percent changes from baseline, rates of patients below a threshold), derivations will be calculated and summaries will be run using conventional units. For other statistics (e.g. values at baseline and over time, absolute changes from baseline), derivations will be presented in both international and conventional units.

Considering the few patients enrolled in the study due to the early termination of the protocol, the efficacy analyses and test for the statistical hypothesis described in the statistical section in the final protocol will not be performed. Instead, descriptive statistics over time will be provided for the efficacy endpoints by treatment group for the Intent-to-Treat population. No formal inferential testing will be performed. The analyses for the mITT population, the analyses of the other secondary endpoints of the NMR-determined particle size and number (biomarkers of TG-rich lipoprotein metabolism, and the analyses of the exploratory endpoints will not be performed.

## **5.8. Analysis of Safety Data**

Safety summaries for the study will be presented by treatment group for the study in the safety analysis set. No formal inferential testing will be performed. Summaries will be descriptive in nature.

All safety analyses will be performed using the baseline definitions described in Section [6.1](#).

### ***General common rules***

All safety analyses will be performed, unless otherwise specified, using the following common rules:

- Safety data in patients who do not belong to the safety analysis set (e.g., exposed but not enrolled) will be listed separately.
- The potentially clinically significant value (PCSV) values are defined as abnormal values considered medically important by the Sponsor according to predefined criteria/thresholds based on literature review and defined by the Sponsor for clinical laboratory tests and vital signs (PCSV version dated January 2009 [[Appendix 10.3](#)]).

Considering that the threshold defined in the PCSV list for monocytes and basophils can be below the ULN, the following PCSV criterion will be used for the PCSV analysis of monocytes and basophils:

- PCSV criterion for monocytes:  $>0.7$  Giga/L or  $>\text{ULN}$  (if  $\text{ULN} \geq 0.7$  Giga/L).
- PCSV criterion for basophils:  $>0.1$  Giga/L or  $>\text{ULN}$  (if  $\text{ULN} \geq 0.1$  Giga/L).
- PCSV criteria will determine which patients had at least 1 PCSV during the TEAE period, taking into account all evaluations including unscheduled or repeated evaluations.
- The treatment-emergent PCSV denominator by treatment group for a given parameter will be based on the number of patients assessed for that given parameter at least once during the TEAE period.

- All measurements, scheduled or unscheduled, fasting or not fasting, will be assigned to Global Analysis Windows defined in Appendix 10.2 /Table 1 in order to provide an assessment for the screening visit through follow-up visit time points.
- For quantitative safety parameters including central laboratory measurements and vital sign scores, descriptive statistics will be used to summarize observed values and change from baseline values by visit.

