#### **Potentially Clinically Significant Value (PCSV)**

If a patient has a missing baseline value, this patient will be grouped in the category “normal/missing at baseline.”

For PCSVs with 2 conditions, one based on a change from baseline value and the other on a threshold value or a normal range, with the first condition being missing, the PCSV will be based only on the second condition.

For a PCSV defined on a threshold and/or a normal range, this PCSV will be derived using this threshold if the normal range is missing; e.g., for eosinophils the PCSV is  $>0.5$  giga/L or  $>\text{ULN}$  if  $\text{ULN} \geq 0.5$  giga/L. When ULN is missing, the value 0.5 should be used.

Measurements flagged as invalid by the laboratory will not be summarized or taken into account in the computation of PCSVs.

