### 10.3. Criteria for Potentially Clinically Significant Values (PCSV)

Parameter	PCSV
Clinical chemistry	
ALT	By distribution analysis:  >2 ULN and baseline $\leq$ 2 ULN >3 ULN and baseline $\leq$ 3 ULN >5 ULN and baseline $\leq$ 5 ULN >10 ULN and baseline $\leq$ 10 ULN >20 ULN and baseline $\leq$ 20 ULN
AST	By distribution analysis:  >2 ULN and baseline $\leq$ 2 ULN >3 ULN and baseline $\leq$ 3 ULN >5 ULN and baseline $\leq$ 5 ULN >10 ULN and baseline $\leq$ 10 ULN >20 ULN and baseline $\leq$ 20 ULN
Alkaline Phosphatase	> 1.5 ULN and baseline $\leq$ 1.5 ULN
Total Bilirubin	> 1.5 ULN and baseline $\leq$ 1.5 ULN > 2 ULN and baseline $\leq$ 2 ULN
Conjugated bilirubin	> 35% total bilirubin (when total bilirubin >1.5 ULN)
ALT and Total Bilirubin	ALT > 3 ULN and Total Bilirubin > 2 ULN and baseline ALT $\leq$ 3 ULN or Total bilirubin $\leq$ 2 ULN

Parameter	PCSV
CPK	> 3 ULN and $\leq$ 5 ULN and baseline $\leq$ 3ULN >5 ULN and $\leq$ 10 ULN and baseline $\leq$ 5 ULN >10 ULN and baseline $\leq$ 10 ULN
Creatinine	$\geq$ 150 $\mu$ mol/L (adults) $\geq$ 30% from baseline $\geq$ 100% from baseline
CLcr (mL/min) (Estimated creatinine clearance based on the Cokcroft-Gault equation)	$\geq$ 15 - <30 (severe decrease in GFR) $\geq$ 30 - < 60 (moderate decrease in GFR) $\geq$ 60 - <90 (mild decrease in GFR) $\geq$ 90 (normal GFR)
eGFR (mL/min/1.73m  ) (Estimate of GFR based on an MDRD equation)	$\geq$ 15 - <30 (severe decrease in GFR) $\geq$ 30 - < 60 (moderate decrease in GFR) $\geq$ 60 - <90 (mild decrease in GFR) $\geq$ 90 (normal GFR)
Uric Acid	
Hyperuricemia:	>408 $\mu$ mol/L
Hypouricemia:	<120 $\mu$ mol/L
Blood Urea Nitrogen	$\geq$ 17 mmol/L
Chloride	<80 mmol/L $\geq$ 115 mmol/L
Sodium	$\leq$ 129 mmol/L $\geq$ 160 mmol/L
Potassium	< 3 mmol/L $\geq$ 5.5 mmol/L
Glucose	
Hypoglycaemia	$\leq$ 3.9 mmol/L and < LLN
Hyperglycaemia	$\geq$ 7 mmol/L (fasted); $\geq$ 11.1 mmol/L (unfasted)
HbA1c	>8%
Albumin	$\leq$ 25 g/L
Hs-CRP	> 2 ULN or $\geq$ 10 mg/L, if ULN not provided
Hematology	
WBC	< 3.0 Giga/L (3000/ mm  ) (Non-Black) < 2.0 Giga/L (2000/ mm  ) (Black) $\geq$ 16.0 Giga/L (16000/ mm  )
Lymphocytes	>4.0 Giga/L

Parameter	PCSV
Neutrophils	< 1.5 Giga/L (1500/ mm  ) (Non-Black) < 1.0 Giga/L (1000/ mm  ) (Black)
Monocytes	>0.7 Giga/L
Eosinophils	> 0.5 Giga/L (500/ mm  ) or > ULN if ULN ≥ 0.5 Giga/L

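### Read literally, the SAP's PCSV criteria for monocytes, basophils and eosinophils reduce to the fixed threshold, so the ULN clause does not do what it was added to do

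*SAP*

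**What the plan says.** **SAP 5.8, General common rules**, defines PCSVs as abnormal values that the sponsor considers medically important. It then departs from the standard list for two parameters, with this reason: "Considering that the threshold defined in the PCSV list for monocytes and basophils can be below the ULN". The replacements are:

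- Monocytes: "PCSV criterion for monocytes: $>0.7$ Giga/L or $>\text{ULN}$ (if $\text{ULN} \geq 0.7$ Giga/L")
- Basophils: "PCSV criterion for basophils: $>0.1$ Giga/L or $>\text{ULN}$ (if $\text{ULN} \geq 0.1$ Giga/L")

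**SAP Appendix 10.3** keeps a plain cut-off of 0.7 Giga/L in its monocyte row. Its eosinophil row already has the two-part form: above 0.5 Giga/L, "or > ULN if ULN ≥ 0.5 Giga/L".

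**SAP 6.3** adds a missing-data convention for criteria built on a threshold and/or a normal range: "this PCSV will be derived using this threshold if the normal range is missing". Its example is eosinophils: "When ULN is missing, the value 0.5 should be used".

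**SAP 5.8.3** applies the criteria to patient measurements in the TEAE period, refers the reader to Appendix 10.3, and reports PCSV incidence overall and by baseline category. Baseline is called normal or abnormal by the same PCSV criterion.

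**The concern.** The reason given in 5.8 is that a fixed cut-off lying below the laboratory's ULN would count in-range results as potentially clinically significant. The replacement should therefore raise the cut-off to the ULN whenever the ULN is higher. Instead it joins two conditions with *or*. The condition on the ULN limits only the second of them, and nothing turns off the first when the ULN is above the fixed value. A programmer who follows the sentence gets back the cut-off that the sentence was written to replace.

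The appendix does not expose the problem. A program written from the monocyte row in 10.3 and a program written literally from 5.8 give identical output, so checking one against the other would show agreement.

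At stake are the PCSV incidence tables and listings for three differential counts, and the split of those tables by baseline status.

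**Working it through.** The SAP gives no figure to reproduce here, so the check is one of logic.

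**Inputs.** The thresholds *t* are 0.7 (monocytes, 5.8), 0.1 (basophils, 5.8) and 0.5 (eosinophils, 6.3 and 10.3), all in Giga/L. Let *x* be the measured value and *u* the ULN. The documents give no value of *u*, so every ULN below is an assumption.

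**Two readings.**

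- Literal: flag if *x* > *t*, or if (*x* > *u* and *u* ≥ *t*).
- Switch: flag if *x* > *u* when *u* ≥ *t*; otherwise flag if *x* > *t*. This is the same as *x* > max(*t*, *u*).

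**The literal rule by cases.**

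- If *u* < *t*, the second clause is off and the rule is *x* > *t*.
- If *u* ≥ *t*, then *x* > *u* implies *x* > *t*, so the second clause adds nothing and the rule is again *x* > *t*.

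The literal rule is therefore *x* > *t* for every ULN.

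**Enumeration.** *x* and *u* were each run over the same grid: 0.3 to 1.5 in steps of 0.01 for monocytes, 0 to 0.4 in steps of 0.005 for basophils, and 0.1 to 1.2 in steps of 0.01 for eosinophils.

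| Parameter | Grid points | Literal differs from *x* > *t* | In-range points flagged, literal | In-range points flagged, switch |
|---|---|---|---|---|
| Monocytes | 121² = 14,641 | 0 | 3,240 | 0 |
| Basophils | 81² = 6,561 | 0 | 1,830 | 0 |
| Eosinophils | 111² = 12,321 | 0 | 2,485 | 0 |

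The in-range counts are the points with *t* < *x* ≤ *u*. They can be checked by hand. There are 80 monocyte grid values above 0.7, so the count is 80 × 81 / 2 = 3,240. For basophils it is 60 × 61 / 2 = 1,830, and for eosinophils 70 × 71 / 2 = 2,485. These are counts of grid points. They are not rates in patients.

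**Monocytes over a range of assumed ULNs.** The test values were 0.65, 0.75, 0.85, 0.95 and 1.05 Giga/L.

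| Assumed ULN | Flagged by the literal rule but not by the switch |
|---|---|
| 0.6 | none |
| 0.7 | none |
| 0.8 | 0.75 |
| 0.9 | 0.75, 0.85 |
| 1.0 | 0.75, 0.85, 0.95 |

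The readings differ only when the ULN exceeds the fixed threshold, and then only for values in the band from the threshold up to the ULN.

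**Baseline.** Because 5.8.3 sorts baseline by the same criterion, a baseline value in that band goes to the abnormal category under the literal rule and to the normal category under the switch.

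**Which reading the SAP intends.** The reason in 5.8 makes sense only if the new rule can differ from the plain threshold. The convention in 6.3 keeps the fixed value for the case of a missing ULN, which suggests that the ULN governs when it is present and at least as high. Both point to the switch. Neither states it: 6.3 settles only the missing-ULN case, and its eosinophil example repeats the same *or* form.

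**The case against.** The strongest reply is that nobody reading 5.8 and 6.3 together would code the literal rule. Section 5.8 says why it departs from the list, it borrows the form already used for eosinophils, and 6.3 makes the fixed value a fallback. On that view the SAP already means max(threshold, ULN), and the point is about wording.

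Much of this stands. The intent can be recovered, so a reader should not infer that in-range values will be flagged. That follows only if the rule is coded as written and the ULN is above the threshold. If the ULN is at or below the threshold, both readings give the same result. Nor is the monocyte row in 10.3 a contradiction, since 5.8 cites the list and expressly overrides it. The absence of a basophil row in the text available may be a conversion loss and is not counted as an error.

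What does not stand is that the wording is therefore adequate. This is more than missing detail: the rule is fully stated, and followed exactly it gives the result that the SAP set out to avoid.

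Two stronger inferences are tempting and unsupported:

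- **That a given share of patients would be wrongly flagged.** The documents give neither a ULN nor a distribution of counts, so no patient-level rate can be derived from them.
- **That a real hematology signal would be hidden.** White cells, neutrophils, lymphocytes, hemoglobin, hematocrit, red cells and platelets have their own criteria and are untouched. Section 5.8.3 also summarizes actual values and changes from baseline. Any over-flagging would follow the same rule in both arms, and 5.8 plans no inferential testing.

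**Conclusion.** The point holds as a drafting defect with a programming risk. Taken literally, the criteria for monocytes, basophils and eosinophils equal plain cut-offs of 0.7, 0.1 and 0.5 Giga/L. This is a logical identity and needs no assumption.

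The consequence is conditional on two things: that the rule is programmed as written, and that the central-laboratory ULN is above the fixed value. If both hold, in-range results enter the PCSV incidence tables and listings, and in-range baselines are classed as abnormal, for these three counts only.

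The practical weight is small. The summaries are descriptive, the study stopped early with few patients, and the primary endpoint is not involved. It is worth correcting because the correction is cheap and leaves the programmer nothing to interpret.

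**What to change.** State each criterion as one threshold:

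- Monocytes: greater than max(0.7 Giga/L, ULN)
- Basophils: greater than max(0.1 Giga/L, ULN)
- Eosinophils: greater than max(0.5 Giga/L, ULN)

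In each case use the fixed value when the ULN is missing, which keeps the convention in 6.3. Put the same wording in 5.8, 6.3 and Appendix 10.3, including the monocyte row and a basophil entry, so that a reader sent from 5.8.3 to the appendix finds the rule that 5.8 intends. Say that the baseline normal/abnormal classification uses the same threshold.

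The cost is a few lines of SAP text and one line of code per parameter. No new data are needed, and nothing is lost beyond what 5.8 already means to exclude. If the tables have already been programmed, check which reading was coded and state it in the abbreviated CSR.
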